1. SPECIFIC AIM

Walking with age becomes both slower and less ‘automated’, requiring more attention and prefrontal resources^{1,2}. As a result, older adults have a greater risk of adverse mobility outcomes and falls. Walking disturbances in the elderly have been linked to changes in both cerebral, in particular small vessel disease (cSVD), and peripheral systems³. There is an urgent need to identify factors that can help compensate for these harmful factors and reduce walking impairments, as there are currently no effective treatments available. Although effective mobility is the end result of the functional capacity of both central and peripheral systems, the brain's unique modulatory and adaptive capacity may provide clues for novel interventions. For example, we have recently discovered that ~20% of older adults maintain fast walking speed even in the presence of age-related cSVD and peripheral system impairments, thus appearing resilient to these harmful factors. Our work suggests that the nigrostriatal dopamine (DA) system may be a source of this resilience. As our recent findings suggest, DA neurotransmission positively predicts walking speed⁴; it also attenuates the negative effects of age-related cSVD and peripheral system impairments on walking speed. These findings are consistent with post-mortem evidence that a combination of loss of nigral DA neurons and cSVD best predict age-related walking impairment⁵⁻⁷. The nigrostriatal DA system plays a critical role in motor control; nigrostriatal DA neurotransmission regulates the automated execution of overlearned motor tasks via its connections with sensorimotor cortical and subcortical areas⁸.

We hypothesize that higher nigrostriatal DA neurotransmission drives resilience to cSVD and peripheral system impairments, via higher connectivity of sensorimotor networks, thus increasing automaticity of walking and reducing prefrontal engagement while walking. Resilience due to the nigrostriatal DA system is a novel and highly promising area of inquiry. Unlike cSVD and brain structural impairments, DA neurotransmission is potentially modifiable, thereby offering novel approaches to treat non-resilient elderly in a targeted fashion. This translational pilot study will use a mechanistic target engagement study mechanisms targeting dopamine using Carbidopa / Levodopa (C-L Dopa) administration in low DA non-resilient elderly to determine change in synaptic DA in relationship to brain imaging connectivity changes and quantitative motor tests.

Exploratory AIM: Does increased DA in non-resilient elderly with parkinsonian signs (incl. gait <1.0msec) improve walking in a mechanistic target engagement study?

Exploratory H1: One week of C-L Dopa treatment will improve walking by increasing DA in elderly with parkinsonian signs.

Exploratory Hy2: C-L Dopa treatment will have a mechanistic effect on functional and metabolic mobility networks in the brain in elderly with parkinsonian signs.

2. BACKGROUND

Rationale. This exploratory mechanistic target engagement study will assess the effect of brief DA supplementation on dopamine availability, nigro-striatal functional connectivity and mobility in a sample of older adults with parkinsonian signs.

The study will screen elderly people for the presence of slow walking (not explained by peripheral or musculoskeletal reasons) and/or other parkinsonian signs. Subjects will be contacted for participation in this study from an existing database in the lab. However, if enough subjects can't be recruited from this database then subjects will be recruited through external sources, such as a flyer posting, online registries, and the University of Michigan Movement Disorders Clinic and other physicians. These subjects will be screened using the telephone screening script, and after this screening they will be brought into the lab to screen for the presence of slow walking and/or other parkinsonian signs. If the clinical assessment does not show evidence for these parkinsonian signs then the person will be excluded from the C-L Dopa and imaging portions of the study (see study outline below).

[figure not shown]
We will record eligibility, adherence, and tolerability to 1-week supplementation (3 days of carbidopa monotherapy and 7 ± 3 days of C-L Dopa at one tablet PO TID for three days followed by an increase to 1.5 tablets PO TID the next day for the next 4 days (± 3 days)), and the effects of C-L Dopa on mechanistic imaging measures of DA sensorimotor functional connectivity and on clinical mobility functions. This translational aim will provide preliminary information about the targeted modifiability of the DA system in non-resilient elderly with parkinsonian signs.

3. RESEARCH PLAN

General Overview:

Study design: Open-label study. An outline of the study is shown in Figure 1. After obtaining informed consent, subjects (max n=60) will undergo a screening exam to assess for parkinsonian signs, including slow walking speed. Elderly subjects without evidence of parkinsonian signs will be excluded from the C-L dopa and imaging portions of the study. Eligible subjects with evidence of parkinsonism (max n=20) will then complete a motor, including gait, cognitive test battery, [¹⁸F]FDG PET scan (optional), and 3T brain MRI (optional) prior to starting the C-L Dopa treatment portion of the study (Refer to Table 1 and Table 3). Subjects will be pre-treated with carbidopa monotherapy 25 mg TID PO for 3 days. Prior to initiating C-L Dopa 25/100 one tablet PO TID for three days subjects will repeat a limited clinical test battery on day 4. Subjects will then increase to 1.5 tablets PO TID on day 7 (i.e., day 4 of C-L Dopa treatment) for the next 4 days (± 3 days). Carbidopa monotherapy will be given to prevent possible side-effects of nausea and participants will stay on 25 mg carbidopa PO TID for the duration of the treatment period of the study. Participants are given the option to be clinically observed in the lab for their first dosage of C-L Dopa. This optional observation would be 60-120 min in length where the participant will take their first dose of C-L Dopa and be monitored by study personnel. After the week-long (± 3 days) C-L Dopa 25/100 trial the complete test battery will be completed. An (optional) [¹¹C]PE2I dopamine PET scan will be performed for assessment of overall nigrostriatal degeneration. This target engagement study will allow for biomechanistic assessment of hypothesized changes in the DA sensorimotor network and will allow us to correlate the C-L Dopa mechanistic effects on DA sensorimotor connectivity changes before/after target engagement as assessed with multimodal graph analytical network methods using optional post-treatment [¹⁸F]FDG and MRI of key relevant circuits related to DA. Dopamine PE2I PET scan will be used for post hoc covariate effects.

Figure 1. Study outline.

Subjects:

Eligibility: Non-resilient elderly non-PD subjects (F/M, age 60 yrs or older) with evidence of mild parkinsonian signs (MPS, slow gait (< 1m/s)). The UPDRS motor component (part III) will be used to assess for evidence of parkinsonian signs, including bradykinesia, tremor, rigidity, and gait disturbances.

Inclusion:

- 1) Age 60 or older (M/F)
- 2) Evidence of mild parkinsonian signs (incl. MPS, slow gait (< 1m/s))

Exclusion:

- 1) Evidence of prior established diagnosis and/or treatment for PD¹³.
- 2) Presence of clinically significant degenerative joint disease and/or neuropathy interfering with proper assessment of the motor UPDRS exam.
- 3) Presence of significant dementia.
- 4) History of stroke with residual clinical deficit interfering with walking.
- 5) For optional MR imaging only: Participants in whom magnetic resonance imaging (MRI) is contraindicated including, but not limited to, those with a pacemaker, presence of metallic fragments near the eyes or spinal cord, or cochlear implant.
- 6) For optional brain imaging only: Severe claustrophobia precluding neuroimaging procedures.
- 7) Participants that have been on monoamine oxidase inhibitors (MAOIs) within 2 weeks prior to starting study.
- 8) Inability to stand or walk without an assistive device
- 9) Hypersensitivity to the carbidopa, levodopa, and tablet components.
- 10) History of myocardial infarction (MI) with residual arterial, nodal or ventricular arrhythmia
- 11) History of peptic ulcer
- 12) Chronic wide angle glaucoma

- 13) Narrow angle glaucoma
- 14) Major psychotic disorder
- 15) Severe cardiovascular or pulmonary disease, bronchial asthma, renal, hepatic or endocrine disease
- 16) Subjects on dopamine D2 receptor antagonists, dopamine depleting agents, and metoclopramide.
- 18) Any other medical history determined by investigators to preclude safe participation.

Study Timeline:

The study will be performed over 2 years with anticipated net recruitment and completion of half of the subjects per year. A milestone of success will be recruitment of 5 subjects who have completed the CL Dopa treatment by the end of year 1. The last 2 months will be used for data analysis and report writing.

Dissemination plan:

Study findings will be published in peer-reviewed journals and presented at scientific meetings.

Design: Within-subject study design using after-before difference measures.

Sample size: This is an exploratory pilot study to generate sample size effects for future larger scale studies, with a net study completion goal of 20 treated subjects.

Impact: Data collected in the proposed study may help identify a novel therapeutic approach to gait slowing in non-resilient elderly with parkinsonian signs, which could have large public health ramifications given the prevalence and serious morbidity of non-specific parkinsonism in the elderly. This project also will elucidate the neurobiology of gait slowing at structural and functional levels of analysis, increasing our understanding of the interplay between these aging-associated processes and the brain network changes underlying late life mobility disorders. Exploring patient-level moderators of response to C-L Dopa may provide useful information to guide differential therapeutics and develop personalized medicine for non-resilient elderly.

Testing:

Table 1: Main components of the Test Battery, including detailed gait and balance assessments

Test	Primary outcome parameter	Admin. Time
Motor: MDS-UPDRS ²	PIGD UPDRS sub-score	15 min
Gait: Timed walking tests (single & dual task gait). Optional: Electronic gait assessments using mats (Zeno Walkways, Protokinetics) and/or sensors (APDM) under single and dual test conditions and challenged gait.	Assessment of standard spatiotemporal gait parameters & variability measures	2 min
Dynamic balance: Mini-BESTest ³ , with optional APDM sensors	Total Mini-BESTest score	15 min
Balance confidence/fear of falling: The Activities-specific Balance Confidence (ABC) scale ⁴	Total ABC score	5 min
		Total: 35 min

Primary Outcome variables:

- (a) Biomechanical gait and postural parameters
- (b) Cognition
- (c) Optional: Brain network connectivity analysis of DA networks using multi-modal MRI and metabolic connectivity based on FDG PET.

Study Treatment:

Carbidopa Monotherapy: Due to the small risk of nausea and vomiting from taking C-L Dopa, all subjects will be pretreated with carbidopa 25 mg orally (PO) three times a day (TID) monotherapy for 3 days prior to starting C-L Dopa.

C-L Dopa administration: A low dose (25/100 1 tablet orally (PO) three times a day (TID) of C-L Dopa immediate release will be used for the first three days of C-L Dopa treatment then if no side-effects will be increased on day 4 of the C-L Dopa treatment to 1.5 pills TID PO. All participants will continue to take carbidopa 25 mg TID PO for the whole duration of the treatment period.

Drug Supplies: Formulation, Preparation and Dispensing

Carbidopa Monotherapy:

Carbidopa will be prepared and dispensed by the Research Pharmacy at the University of Michigan.

C-L Dopa administration:

C-L Dopa will be prepared and dispensed by the Research Pharmacy at the University of Michigan.

Drug Storage and Drug Accountability

Carbidopa Monotherapy: Drug will be stored and accounted for at the Research Pharmacy at the University of Michigan per their established standing operating procedures.

C-L Dopa administration: Drug will be stored and accounted for at the Research Pharmacy at the University of Michigan per their established standing operating procedures.

Concomitant Medications

Use of both carbidopa monotherapy and C-L Dopa, has been contraindicated with concurrent use with nonselective monoamine oxidase inhibitors (MAOIs) or use within the last 14 days.

Other Considerations

High protein diets have the potential to impair C-L Dopa absorption as the levodopa ingredient competes with certain amino acids for transport across the gut wall or across the blood-brain barrier. For this reason, participants will be instructed to take the study drugs at least ½ hour before each meal (i.e., breakfast, lunch & supper). However, the pre-meal intake of these drugs can be combined with non-proteinous supplements, like fruit juices or fruits (banana, apple sauce, etc.).

Clinical Testing:

Clinical assessment (see also Table 3) includes a general demographic, medical and, neurological examination, the measurement of visual acuity, (optional) visual contrast sensitivity (Rabin test), (optional) color blindness (Munsell 15), orthostatic vital signs, weight and height in all subjects, general motor assessment, including the Movement Disorder Society revised UPDRS examination (13), modified Hoehn & Yahr (14) to provide assessment of general motor impairments of PD. Questionnaires to assess overall sedentarism and physical activity will be administered. Detailed cognitive testing will also be performed.

Clinical and functional assessment of motor features:

Several well-validated balance, gait, and fall-associated scales and tests will be used to further assess functional mobility in PD (see Table 3). In addition to these motor examinations we will also use questionnaires to assess for the presence of gait festination and freezing of gait¹⁵⁻¹⁷. In addition, finger tapping and Grooved Pegboard testing will be used to provide quantitative measures of upper limb bradykinesia and motor dexterity. Foot tapping will be used as a measure of lower limb bradykinesia. A specialized mobility and postural control test battery to capture gait and postural functions will also be performed. Some tasks may be performed while performing a secondary cognitive task (e.g. counting backwards by 3s).

Biological samples:

Saliva samples may be collected for analysis of dopamine and other related genotypes. Samples will be processed and analyzed at laboratories the Department of Human Genetics, or at other intra- or extramural institutions.

Neurocognitive and functional status assessments:

Table 2 provides an overview of the detailed neuropsychological examination. We will assess global cognitive changes over time based on the MMSE¹⁸, MoCA¹⁹, and a composite z-score encompassing the major cognitive domains from the test battery.

Table 2. Components of the neuropsychological test battery

Overall mental status	Optional: Mini Mental State Exam ¹⁸ Montreal Cognitive Assessment Scale ¹⁹
Attention	D-KEFS: Trail Making Test, Stroop Color Word Interference Test ²⁰
Learning & Memory	Optional: California Verbal Learning Test – II ²¹
Executive/Working Memory	D-KEFS: Trail Making Test D-KEFS: Trail Making Test ²⁰
Information processing speed	Digit Symbol test, Optional: Reaction time Optional: Falling stick test

MR imaging (optional): MR imaging will be performed on a 3 Tesla Philips Achieva system (Philips) utilizing a 15-channel head coil and the 'ISOVOX' exam card protocol primarily designed to yield isotropic T₁ spoiled gradient (SPGR) spatial resolution. This protocol consists of a number of different sequences including a standard T₁-weighted series of a 3D inversion recovery-prepared turbo-field-echo will be performed in the sagittal plane with repetition time/echo time/inversion time = 9.8/4.6/1041 ms; turbo factor = 200; single average; field of view = 240 x 200 x 160 mm; acquired matrix = 240 x 200.

Slices (n = 160) will be reconstructed to 1mm isotropic resolution. This sequence maximizes contrast among grey matter, white matter and CSF and provides high resolution delineation of cortical and subcortical structures. Other standard sequences include FLAIR, DTI, resting state functional connectivity MRI, or other relevant series. The brain MRI scan can be performed on the same day as the clinical assessment or on a separate day prior to starting study drug treatment.

PET imaging (optional): All PET data will be acquired at the University of Michigan PET facility on a Siemens BioGraph TruePoint Model 1094 PET/CT scanner, which produces 109 slices, has an axial field-of-view of 22.0 cm with slice thickness of 2.027 mm, and intrinsic image resolution 4.2 mm full-width at half maximum (FWHM). Image reconstruction for both tracers will be done with fully 3D-iterative OSEM, using 4 iterations, 16 subsets, and post-reconstruction files of 3.0 mm FWHM, yielding images of ~5.0 FWHM. One low-dosage CT scan (130 kVp, 30 eff mAs, 6 x 3mm collimation, pitch =1, rotation time =0.6 second) of the head will be performed prior to each brain PET scan for attenuation correction purposes. "As low as reasonably achievable" (ALARA) techniques will be utilized to minimize subject radiation exposure. Subjects will be studied supine, with eyes and ears unoccluded, resting quietly in a dimly lit room. [¹⁸F]FDG and [¹¹C]PE2I PET ligands are non-approved radiopharmaceutical that will be used in accordance with Food and Drug Administration regulations (21 CFR 361.1). All tracers are prepared following standard synthesis routines at the University of Michigan PET Chemistry and Cyclotron facilities.

Daily life activity levels (optional): Overall activity levels during medication therapy will also be assessed. Subjects will be asked to wear an accelerometer based actigraphy device (Actigraph or ActivPAL) for the duration of the carbidopa monotherapy and carbidopa-levodopa mechanistic study.

Compliance Monitoring Phone Call: A compliance phone call will be performed by a research staff member during the 7±3 C-L Dopa medication stage.

Timeline: Refer to table 3 for timeline and test details. Day 0 may be completed over multiple visits. Once all tasks listed under Day 0 are completed Day 1 will start. Day 9(±3) tasks will be performed while participant is still taking C-L Dopa and may require multiple visits.

Table 3. Detailed components, test protocol, and timeline

	Pre-Rx (Day 0) Baseline	Day 1-3	Day 4	Day 4-6	Day 7-10(±3)	Day 10 (±3)
Informed Consent	✓					
Demographic Information	✓					
Inclusion/Exclusion Criteria	✓					
Clinical & Neurological Assessment	✓					✓
Optional: Saliva sample	✓					
MDS-UPDRS	✓		✓			✓

Mini-BESTest (optional: APDM Sensored)	✓		✓			✓
Regular timed walking single & dual-task Optional: Zeno Walkways Single, Dual, and challenged gait Task	✓		✓			✓
Optional: APDM Mobility assessments	✓		✓			✓
Optional: Oculovestibular	✓					✓
Pegboard	✓		✓			✓
Finger tapping	✓		✓			✓
Foot tapping	✓		✓			✓
Optional: Reaction Time Test/ Optional: React Stick Test	✓					✓
Optional: Four Square Step Test	✓					✓
Optional: Maximum Step Length Test	✓					✓
Activity questionnaire	✓					✓
Balance confidence/fear of falling: The Activities-specific Balance Confidence (ABC)	✓					✓
Optional: New-FOGQ	✓					✓
Optional: Short FES-I	✓					✓
Sensonics UPSIT	✓					optional: ✓
Optional: Eyetech OCAT	✓					✓
MoCA	✓		✓			✓
Optional: MMSE	✓					✓
DKEFS-STROOP	✓		✓			✓
DKEFS-TMT	✓		✓			✓
Optional: CVLT	✓					✓
Information processing	✓		✓			✓
General Feeling Questionnaire	✓					✓
Apathy Evaluation Scale	✓					✓
Geriatric depression scale	✓					✓
Spielberger anxiety scale	✓					✓
Optional: BPRS	✓					✓
Epworth Sleepiness Scale	✓					✓

Mayo Sleep Questionnaire (22)	✓					✓
FSS	✓					✓
Optional: Insomnia Questionnaire	✓					✓
Optional: Somnolence VAS	✓		✓			✓
Snellin Test	✓					✓
Optional: Rabin	✓					✓
Adverse event assessment	✓	✓	✓	✓	✓	✓
Optional MRI	✓					✓
Optional FDG PET	✓					✓
Optional PE2I PET (will occur only 1 time)	✓					✓
Optional DEXA	✓					
Optional 90-120 minute observation (post medication) after first intake				✓		
Carbidopa Monotherapy 25 mg TID PO		✓	✓	✓	✓	✓
C-L Dopa 25/100 1 tablet PO TID			✓	✓		
C-L Dopa 25/100 1.5 tablet PO TID					✓	✓
Compliance Monitoring Phone Call		✓			✓	
Optional: Actigraphy		✓	✓	✓	✓	✓

Analysis:

Statistical analysis: We anticipate that 90% of eligible subjects will complete the 1-week C-L Dopa supplementation; the effect of C-L Dopa administration on brain connectivity and mobility measures will be tested using a repeated measures design.

Comments: This exploratory open label pilot study will investigate the feasibility for future clinical trials of C-L Dopa therapy in non-resilient elderly with parkinsonian signs.

Data safety-monitoring plan: This study will adhere to a data safety-monitoring plan where the principal investigator will be responsible for regular (at least annual) monitoring of general progress of the study, such as subject recruitment, perform interim statistical analysis on the data (only when statistically feasible), review of outcome and adverse event data to determine whether there is any change to the anticipated benefit-to-risk ratio (which may require modification or termination of the study protocol), assessment of external scientific or medical developments that may have an impact on the safety of study participants or the ethics of the study. [name], Assistant Professor of Neurology, will serve as an independent safety officer and will review twice yearly safety reports. The monitoring process will also include a review of study procedures aimed at the protection of the privacy of the research subjects and confidentiality of the research data. Adverse events will be reported to the IRB adverse events reporting guidelines. If the protocol needs to be modified or there is a change in the level of risk to subjects for this study, a

modification submission will be prepared for review by the IRB. All data collected on research subjects will be kept confidential as detailed above.

Risks (as described in informed consent form):

The known or expected risks will be defined as: Likely - occurring in more than 25% of people (more than 25 out of 100 persons); Common – occurring in 10% - 25% of people (in 10 to 25 out of 100 persons); Infrequent - occurring in 1 - 10% of people (1 to 10 out of 100 people); Rare - occurring in less than 1% of people (fewer than 1 out of 100 persons); or Very Rare - occurring in less than 0.1% of people (fewer than 1 in 1,000 persons).

The known or expected risks will be described in normal script.

The actions that the researchers take to minimize these risks will be described in italic script, as demonstrated in this paragraph.

General risks:

There is a very rare risk of breach of confidentiality, which may affect privacy, self-esteem, social standing, employability, and insurability.

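### Visit is not masked when the optional gait recordings and scans are processed offline, which leaves a bias open that could be closed cheaply

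*Combined protocol and SAP*

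**What the plan says.** In the combined protocol and SAP, section 3 (Research Plan, General Overview) states "Study design: Open-label study". The design line later in that section reads "Design: Within-subject study design using after-before difference measures", and no concurrent control group is described. The first exploratory hypothesis in section 1 is directional: it expects walking to improve on treatment.

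The list of primary outcome variables opens with (a) "Biomechanical gait and postural parameters" and ends with (c) "Optional: Brain network connectivity analysis of DA networks using multi-modal MRI and metabolic connectivity based on FDG PET". Table 1 gives timed walking as the non-optional gait test and then adds "Optional: Electronic gait assessments using mats (Zeno Walkways, Protokinetics) and/or sensors (APDM) under single and dual test conditions and challenged gait". The gait output is described only as "Assessment of standard spatiotemporal gait parameters & variability measures". The imaging change is to be examined "as assessed with multimodal graph analytical network methods", and the list of MRI sequences is left open.

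Table 3 places gait testing at baseline, Day 4 and Day 10 (±3), and MRI and FDG PET at baseline and Day 10 (±3). PE2I PET is done only once, so it yields no before/after pair. The Analysis section names a repeated measures design and anticipates 90% completion. The data safety-monitoring plan allows the principal investigator to run interim analyses where feasible. It also appoints an independent safety officer, who reviews safety reports.

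**The concern.** Participants and examiners in an open-label study know the treatment. Offline processing is different: a walkway file or a scan can be handled by someone who does not know which visit it came from. The plan does not use this opportunity.

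If processing includes decisions such as which walks or strides to drop, which scans fail on motion, or where a region boundary lies, a processor who can see the visit may lean towards the expected result without intending to. In a before/after comparison with no control group, a lean of that kind adds directly to the estimated treatment effect.

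The pilot exists to provide effect sizes for larger studies. A distorted estimate would therefore carry into the planning of the next trial as well as into this report.

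**Working it through.** **Step 1. Look for any masking.** No figure in the plan bears on this point, so the first check is textual.

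| Place | What it settles | Visit hidden, files coded, or values locked before unmasking? |
|---|---|---|
| General Overview | Open label; graph-based network methods named in general terms | Not stated |
| Testing, Table 1 | Devices; gait output in general terms | Not stated |
| MR imaging and PET imaging | Scanners, sequences, reconstruction settings | Not stated |
| Analysis | Repeated measures design | Not stated |
| Data safety-monitoring plan | Safety review; possible interim analyses | Not stated for outcome data |

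None of these sections gives a rule for rejecting walks, a motion criterion, a set of regions, a graph threshold or an automated pipeline. None says who processes the data.

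**Step 2. Which data are exposed.** Mats, sensors, MRI and FDG PET are all optional. The point covers only participants who have them at both ends of the comparison. The timed walk, UPDRS and Mini-BESTest are scored at the visit, so coding files afterwards would not protect them.

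**Step 3. Sensitivity to an assumed shift.**

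Inputs from the plan: at most 20 treated participants (General Overview) and 90% completion (Analysis), giving 0.90 × 20 = 18 pairs. This is an upper bound, because the measures are optional and no uptake figure is given.

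Assumed inputs: a two-sided 5% paired t test (the plan states no level); a true change of zero; a processing shift of b SDs of the paired change, with b = 0.10, 0.20 or 0.30; and 10 pairs as a lower-uptake case.

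Formulas: the standard error of the standardised mean change is 1/√n. The test statistic follows a noncentral t distribution with n − 1 degrees of freedom and noncentrality b√n. The false-positive rate is the probability that it falls beyond either critical value.

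- n = 18: standard error 1/√18 = 0.236.
- n = 10: standard error 1/√10 = 0.316.

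| b | b√18 | Rate, 18 pairs | b√10 | Rate, 10 pairs |
|---|---|---|---|---|
| 0 | 0 | 5.0% | 0 | 5.0% |
| 0.10 | 0.42 | 6.9% | 0.32 | 5.9% |
| 0.20 | 0.85 | 12.6% | 0.63 | 8.8% |
| 0.30 | 1.27 | 22.5% | 0.95 | 13.6% |

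**Step 4. Effect on later planning.** Suppose a true standardised paired change of 0.3 were reported as 0.5, which is a shift of 0.2. For 80% power at two-sided 5%, the number of pairs is roughly (1.96 + 0.84)²/d² + 1.96²/2.

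- d = 0.5: 7.84/0.25 + 1.92 = 33.3, so 34 pairs.
- d = 0.3: 7.84/0.09 + 1.92 = 89.0. The unrounded normal values give 89.1, so 90 pairs.

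The next study would be planned with 34 pairs when it needed about 90. The 0.3 and 0.5 are again illustrative.

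**The case against.** The strongest reply is that silence is not an error. The plan openly describes a small, uncontrolled, open-label pilot and contradicts itself nowhere on this point. Masked processing is good practice, but a short exploratory protocol may not mention it. That is fair, and it is why the point ranks as an improvement. It does not dispose of the point, because an open label governs what is known at dosing and testing and does not prevent files from being coded later.

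The second reply is that the mechanism is inferred. The documents do not describe manual editing. If one automated pipeline, atlas and threshold were applied to every scan, those choices could not differ between visits of the same person. This stands. A graph threshold chosen once for the whole dataset is mainly a matter of pre-specification, and hiding visit labels deals with it only in part.

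The third reply concerns reach. A reader might infer that the whole of primary outcome (a) is exposed. The documents do not support that, since the instrumented gait measures are optional and the required timed walk is scored at the visit. A reader might also infer that the same people process both files knowing which is which. The documents do not say who does the work.

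Finally, masking leaves untouched the larger weaknesses of an uncontrolled before/after design: participant expectation, practice effects and regression to the mean. That also stands.

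**Conclusion.** The point holds for the optional instrumented part of outcome (a) and for optional outcome (c). In the text available, visit is not masked during offline processing, so any judgement exercised there could favour the after-treatment files and bias the pilot's effect sizes. Because some pages were removed before review, the absence of masking is established only for the text that was seen.

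The documents show that such bias is possible. They do not show that it will occur or how large it would be. It would be tempting to read 6.9% to 22.5% as the study's false-positive rate. That is not supported: the shift, the 5% level and the test are all assumptions, and 18 pairs is the most the plan's own completion figure allows. With an assumed 10 pairs the range is 5.9% to 13.6%. These figures show sensitivity only.

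**What to change.** Add a short statement to the Analysis section:

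- Gait-mat and sensor files, including those from Day 4, and MRI and FDG PET files are given random codes before processing. Visit and date are removed from file names and headers.
- Exclusions, regions and derived values are completed and locked under code. One pipeline and one graph threshold are fixed for all scans before unmasking.
- A study coordinator holds the visit key and releases it only after the lock. If an interim analysis uses these outcomes, the values concerned are locked first.
- The timed walk, UPDRS and Mini-BESTest remain open and are labelled so in the report.
- If processing is fully automated, the plan should say so and name the pipeline.

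The cost is a file-renaming script, some file handling and a delay before unmasked analysis. No extra reader, visit or participant burden is needed.
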